## Appendix 10 – modified Electronic Cigarette Evaluation Questionnaire - Ext (mECEQ-E)

**ELECTRONIC CIGARETTE EVALUATION QUESTIONNAIRE- Ext modified**

Have you used any ELECTRONIC cigarettes since your last visit?

- No: Skip questionnaire
- Yes: Please answer the following questions based on the **FIRST** use of the day on the last day you used the ELECTRONIC cigarette.

	Not at all	Very little	A little	Moderately	A lot	Quite a lot	Extremely
1. Was it satisfying?							
2. Did it taste good?							
3. Did it make you dizzy?							
4. Did it calm you down?							
5. Did it help you concentrate?							
6. Did it make you feel more awake?							
7. Did it reduce your hunger for food?							
8. Did it make you nauseated?							
9. Did it make you feel less irritable?							
10. Did you enjoy the sensations of the smoke in your throat and chest?							
11. Did it immediately reduce your craving for cigarettes?							
12. Did you enjoy smoking?							

Please answer the following questions based on the use of the ELECTRONIC cigarette **immediately after a meal**.

- Did not use the ELECTRONIC cigarette **immediately after a meal**: Skip section

	Not at all	Very little	A little	Moderately	A lot	Quite a lot	Extremely
1. Was it satisfying?							
2. Did it taste good?							
3. Did it make you dizzy?							
4. Did it calm you down?							
5. Did it help you concentrate?							
6. Did it make you feel more awake?							
7. Did it reduce your hunger for food?							
8. Did it make you feel nauseated?							
9. Did it make you feel less irritable?							

10. Did you enjoy the sensations of the smoke in your throat and chest?							
11. Did it immediately reduce your craving for cigarettes?							
12. Did you enjoy smoking?							

Please answer the following questions regarding **all other times you used the ELECTRONIC cigarette** on the last day you used the ELECTRONIC cigarette.

	Not at all	Very little	A little	Moderately	A lot	Quite a lot	Extremely
1. Was it satisfying?							
2. Did it taste good?							
3. Did it make you dizzy?							
4. Did it calm you down?							
5. Did it help you concentrate?							
6. Did it make you feel more awake?							
7. Did it reduce your hunger for food?							
8. Did it make you nauseated?							
9. Did it make you feel less irritable?							
10. Did you enjoy the sensations of the smoke in your throat and chest?							
11. Did it immediately reduce your craving for cigarettes?							
12. Did you enjoy smoking?							

Appendix 11 – Halo G6 Flavor Assessment Questionnaire

**HALO G6 Flavor Assessment Questionnaire**

Now that you have tried the two flavors of HALO G6, are you willing to switch to either of these flavors?

(CHECK ONE RESPONSE ONLY)

YES \_\_\_\_\_

No \_\_\_\_\_

If YES, which flavor would you like to use:

Tribeca (tobacco) \_\_\_\_\_

Mint \_\_\_\_\_

---

## INSTRUCTIONS FOR PROPER USE OF BUPROPION (ZYBAN)

### How does it work?

This medicine helps a person to stop smoking by reducing the desire (urge) to smoke.

### How do I take this medicine?

1. Take bupropion exactly as directed. The blister packs are designed to help you take the medicine properly.
  - a. For the first 3 days, take one tablet (150 mg) in the morning.
  - b. For the rest of the time, take two tablets (150 mg x 2) in the morning.
  - c. Only change your medicine at the direction of the study personnel or if you have a serious concern.
2. Do not crush, chew or split the tablet
3. Take bupropion with a full glass (8 ounces) of water. You may take bupropion with or without food (do NOT drink alcohol with bupropion).
4. We will schedule you to start taking bupropion about 7 days before your actual switch date (the day you stop smoking and only use electronic cigarettes).
5. If you forget to take a dose of bupropion, take it as soon as you remember. If it is almost time for your next dose (less than 6 hours), just wait and take your next dose at the regular time. Do NOT take an extra dose to make up for the dose you forgot.
6. Keep this medication in a safe place, AWAY FROM CHILDREN. It should be stored at room temperature (not in your car) and away from direct sun, excessive heat, cold, or moisture. You MUST return any unused medication.

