## 1.1 STUDY DESIGN AND PLAN

This open-label study will explore the impact of combination zonisamide and bupropion on the process of switching from combustible cigarettes (CC) to an e-cigarette.

Zonisamide is an FDA-approved medication with an anti-seizure indication, with daily doses usually ranging from 100 mg/day to 600 mg/day). It has multiple mechanisms of action, which include inhibiting activation of voltage-gated sodium channels at therapeutic levels. In addition, zonisamide also inhibits glutamate-mediated neurotransmission and enhances inhibitory GABA-ergic as well as serotonergic neurotransmission. It also enhances dopamine levels in the striatum, which in theory could help replace the desired effects of addictive drugs such as nicotine that also raise striatal dopamine. Topiramate, a drug sharing some actions with zonisamide, has been shown to facilitate smoking cessation and prevent post-cessation weight gain. Zonisamide has been shown to reduce ad libitum smoking as well as to relieve craving for cigarettes. It also has been shown to decrease anger, restlessness and impatience during smoking abstinence.

The zonisamide/bupropion combination has an additional rationale in that the potential side effects of each agent are offset by the other. For example, bupropion is associated with side effects of agitation and insomnia while zonisamide has sedative properties. Conversely, the side effects of zonisamide include sedation, which are expected to be partially offset by bupropion's stimulant actions. The combination of bupropion and zonisamide has been shown to be well tolerated in studies of weight loss produced by this drug combination.

There is no therapeutic intent in that smokers' nicotine/tobacco dependence will not be treated; the goal is to switch from one form of nicotine/tobacco dependence (CC) to dependence on a different tobacco product (e-cigarettes).

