### 6.3 DOSE ADJUSTMENT PROCEDURES

Zonisamide will be dispensed in the form of a 50 mg capsules. Adjustments may be made to the timing of the dose (AM or PM) or the amount (1 or 2 capsules) depending on the somnolence/activation experienced by each individual participant. Initially, both bupropion and zonisamide will be taken in the morning. Should participants experience significant drowsiness, the medical providers (MD/PA) may change the dosing to nighttime (2 hours prior to bedtime) or decrease the dose to one 50 mg capsule per day. All dosing adjustments will be approved by the Medical Director for this study.

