### 7.1 DESCRIPTION OF BUPROPION

Bupropion inhibits reuptake of both noradrenaline and dopamine. This medication has been approved as an antidepressant for over 20 years. The Food and Drug Administration approved the use of bupropion for smoking cessation in 1997. It is only one of two medications currently approved by the FDA for this purpose. The combination of bupropion and zonisamide has been studied as a treatment for weight loss in obese adults. The usual dose for bupropion for smoking cessation is 150 mg once a day for 3 days, followed by 300 mg once a day for 7 to 12 weeks. The maximum prescribed dose for bupropion is 450 mg a day, which is the maximum dose for treating major depressive disorder and attention deficit hyperactivity disorder for adults.

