### 7.3 DOSE ADJUSTMENT PROCEDURES

Bupropion will be dispensed in the form of a 150 mg extended release tablet, initially one tablet daily for 3 days, followed by 2 tablets daily until End of Study. Extended release tablets have a half-life that supports once daily dosing. Combining this medication with zonisamide will decrease the risk for side-effects, allowing for daily dosing, which will likely improve compliance. Adjustments will be made depending on the side-effects experienced by each individual participant. Initially, both bupropion and zonisamide will be taken in the morning. Should participants experience significant activation during the day, the medical providers (MD/PA) may either adjust the dose down to 150 mg daily or split the dose (150 mg taken twice daily which is normal dosing for smoking cessation). All dosing adjustments will be approved by the Medical Director for this study.

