#### 9.1.1 Zonisamide

The most common adverse effects of zonisamide include somnolence, dizziness, nausea, heartburn, constipation, weight loss, changes in taste, dry mouth, drowsiness and headache. In prior clinical trials of zonisamide, discontinuation rates varied between 4% to 24% due to adverse effects (these studies

administered daily doses of 300 to 500 mg). This study will evaluate zonisamide at a maximum dose of 100 mg daily.

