### 9.1.2 Bupropion

Common adverse effects of bupropion (occurring greater than 5% more than placebo) include headache, dry mouth, nausea, insomnia, constipation, and dizziness. These adverse effects were observed for doses ranging from 300 mg to 400 mg daily. Adverse events leading to discontinuation in clinical trials occurred at a relatively low rate, with 7% drop-out for all doses, 9% drop-out at the 300 mg dose, and 11% drop-out for the 400 mg dose. This study will utilize bupropion at a maximum dose of 300 mg daily.

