### How do I take this medicine?

1. Take zonisamide exactly as directed. The blister packs are designed to help you take the medicine properly.
  - a. Take 2 capsules (50 mg each, total of 100 mg) in the morning.
  - b. Only change your medicine at the direction of the study personnel or if you have a serious concern.
2. Do not take this medicine if you have a severe allergy to sulfa drugs (like Bactrim, Septra, Diabeta).
3. Do not crush, chew, open or split the capsule.
4. Take zonisamide with a full glass (8 ounces) of water. Zonisamide can be taken with or without food (do NOT drink alcohol with zonisamide).
5. We will schedule you to start taking zonisamide about 7 days before your actual switch date (the day you stop smoking and only use the electronic cigarette).
6. If you forget to take a dose of zonisamide, take it as soon as you remember. If it is almost time for your next dose (less than 6 hours), just wait and take your next dose at the regular time. Do NOT take an extra dose to make up for the dose you forgot.
7. Keep this medication in a safe place, AWAY FROM CHILDREN. It should be stored at room temperature (not in your car) and away from direct sun, excessive heat, cold, or moisture. You MUST return any unused medication.

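### The 6-hour missed-dose cut-off in the participant handouts allows two full once-daily bupropion doses (300 mg each) only 6 hours apart

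*Combined protocol and SAP*

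**What the plan says.** The bupropion handout (Instructions for Proper Use of Bupropion, item 5 on how to take the medicine) says to take a forgotten dose when it is remembered. It then gives the exception: "If it is almost time for your next dose (less than 6 hours), just wait and take your next dose at the regular time". A last sentence warns against an additional dose to compensate. Item 6 of the zonisamide handout gives the same rule with the same cut-off.

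The schedule is one dose a day. Section 6.3 states: "Initially, both bupropion and zonisamide will be taken in the morning". Section 7.3 says the same and supports it with: "Extended release tablets have a half-life that supports once daily dosing". From day 4 the bupropion dose is two 150 mg tablets together. Zonisamide is two 50 mg capsules together.

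The ceilings are as follows:
- Bupropion in this study, Section 9.1.2: "This study will utilize bupropion at a maximum dose of 300 mg daily".
- Bupropion in general, Section 7.1: "The maximum prescribed dose for bupropion is 450 mg a day".
- Zonisamide in this study, Section 9.1.1: "This study will evaluate zonisamide at a maximum dose of 100 mg daily". Section 1.1 describes the drug "with daily doses usually ranging from 100 mg/day to 600 mg/day".

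No section sets a longer minimum interval between once-daily doses, limits a make-up to the day of the missed dose, or delays the next regular dose after a late one.

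**The concern.** With one dose every 24 hours, a 6-hour cut-off leaves the missed dose open for 18 hours, and the next full dose still follows on time. The late dose and the regular dose can then fall close together, although the regimen was chosen because the tablet suits once-daily use. Section 7.3 deals with significant daytime activation by lowering bupropion or splitting it into two 150 mg doses. The handout permits two 300 mg doses within 6 hours.

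What is at stake is participant safety and agreement between a participant-facing instruction and the protocol's own dose limits. The adverse-effect and drop-out figures in Section 9.1.2 are for daily doses up to 400 mg, so they do not describe a 600 mg day. The endpoint definition, sample size, error rates and analysis are not involved.

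**Working it through.** **Inputs.** Cut-off c = 6 h (both handouts). Bupropion 2 × 150 = 300 mg once daily from day 4 (handout, Section 7.2). Zonisamide 2 × 50 = 100 mg once daily (handout, Section 6.2). Ceilings: 300 and 450 mg/day for bupropion (Sections 9.1.2 and 7.1), 100 mg/day for zonisamide (Section 9.1.1). The documents say only that doses are taken in the morning, so the clock time h is an assumption, varied here from 05:00 to 10:00.

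**Plan's own figure.** With no dose missed, 2 × 150 = 300 mg a day, which matches the stated study maximum.

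**Minimum gap.** A dose missed at h is followed by the next at h + 24. A make-up is allowed while at least c hours remain, so the latest make-up is h + 24 − c. With c = 6 this is h + 18, and the gap to the next full dose is (h + 24) − (h + 18) = 6 h. This result does not depend on h or on how a day is counted.

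**After-midnight make-up.** The latest make-up passes midnight when h + 18 > 24, that is, when h is later than 06:00. The window after midnight lasts h − 6 hours.

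| Regular time | Latest make-up, c = 6 | Window after midnight | Highest calendar-day bupropion | Latest make-up, c = 12 |
|---|---|---|---|---|
| 05:00 | 23:00 same day | none | 300 mg | 17:00 |
| 06:00 | 00:00 | midnight only | 600 mg | 18:00 |
| 07:00 | 01:00 | 1 h | 600 mg | 19:00 |
| 08:00 | 02:00 | 2 h | 600 mg | 20:00 |
| 09:00 | 03:00 | 3 h | 600 mg | 21:00 |
| 10:00 | 04:00 | 4 h | 600 mg | 22:00 |

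**Size against the ceilings.** 300 + 300 = 600 mg, which is 600/300 = 2.0 times the study maximum and 600/450 = 1.33 times the maximum prescribed dose. Zonisamide: 100 + 100 = 200 mg, 2.0 times its study maximum but inside the usual range in Section 1.1.

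**Lower doses.** In the first three days the bupropion sum is 150 + 150 = 300 mg. A day-3 dose made up on day 4 gives 150 + 300 = 450 mg. A participant reduced to 150 mg daily reaches at most 300 mg.

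**Two-day total.** One missed dose taken late plus one regular dose is 600 mg of bupropion over two days, as planned.

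**With c = 12.** The latest make-up is h + 12 and the minimum gap is 12 h. No make-up can fall after midnight for any h before 12:00, so the calendar-day total stays at 300 mg. On a rolling count, 20:00 then 08:00 still puts 600 mg within 24 h. Any make-up followed by the regular dose does so under either cut-off.

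**The case against.** The strongest reply is that the ceilings describe regimens. On that reading, a late dose is still the missed day's dose, one dose counts per treatment day, and nothing is exceeded. The protocol does not define daily or say that doses are counted from midnight, so a reader who infers that the handout plainly breaches the 300 mg and 450 mg limits goes further than the text allows. The breach holds only under calendar-day counting, with a regular time after 06:00 (or a make-up exactly at midnight for a 06:00 dose) and a make-up taken after midnight.

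The scenario is also narrow. Section 8.5 labels the daily message a PM SMS, and Section 8.6.2 has it ask whether that morning's drugs were taken. Answering is paid (Section 4.7), and blister packs help a participant notice a missed dose. All of this makes recall before midnight more likely. It does not exclude late recall, because the message may go unread for hours: under Section 4.8.3 replies are accepted until the next message.

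Three further inferences lack support. The documents give no clinical effect for one closely spaced pair of doses and no frequency, so they do not show that a 6-hour gap causes harm. Zonisamide does not carry equal weight, since 200 mg exceeds only its study maximum. Participants moved to night-time zonisamide or split bupropion cannot be counted as further breaches, because the documents do not show which missed-dose instruction would then apply.

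The warning against an additional dose does not answer the point. If it barred every late dose, it would contradict the first sentence of the same item and leave the 6-hour test with no purpose.

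**Conclusion.** The concern holds as a minor safety point about bupropion. The firm finding is the gap: following the handout exactly permits two full 300 mg doses 6 hours apart, whatever the clock time. The 600 mg calendar day is conditional on the counting rule, the assumed dose time and an after-midnight make-up, and it applies from day 4 at the full once-daily dose. It is unlikely in practice, and its clinical effect cannot be judged from these documents. No section establishes 12 hours as the correct interval, so that figure is a proposal. A reader might infer that a longer cut-off keeps every 24-hour period at 300 mg. It does not: it widens the minimum gap and, for dose times before noon, keeps the make-up out of the next calendar day.

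**What to change.** For once-daily morning dosing, change the cut-off in both handouts from 6 to 12 hours before the next dose, with the Medical Director confirming the interval. Check the choice against the time of the PM SMS, which the documents do not give. For an 08:00 dose, a 12-hour cut-off ends make-ups at 20:00, so a later message could only prompt doses that must be skipped. A 10-hour cut-off would end them at 22:00 and still prevent after-midnight make-ups for dose times before 10:00.

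A same-day rule alone is not enough: with a 05:00 dose it would allow 23:59 then 05:00, a gap of about 5 hours. If same-day wording is wanted, combine it with the minimum interval.

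Give participants moved to night-time zonisamide or split bupropion their own missed-dose line when the schedule changes. The 12-hour rule must not be carried over to a 12-hourly split (for example 08:00 and 20:00), where it would bar every make-up.

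The cost is one phrase in each handout, the added line for changed schedules, and an IRB submission. The make-up period falls from 18 to 12 hours, so doses remembered more than 12 and up to 18 hours late would be skipped.

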### Precautions

Some people have reported changes in behavior, agitation, depression, thoughts of suicide, or hostility. If you experience any of these issues, please call Rose Research Center and speak with one of our helpful staff [contact]). You may also call the 24-hour emergency advice line and speak with our study physician [contact]) if you feel this is an emergency.

As with most any medication, there is a risk of having an allergic reaction to bupropion. This can be serious, especially if you experience swelling of the face, mouth, tongue, or throat which causes difficulty breathing. If you have any of these symptoms, stop taking bupropion and get medical attention right away. Inform the staff at Rose Research Center AFTER you obtain medical care for these symptoms.

You should tell the staff at Rose Research Center if you have any allergies to medicines, including bupropion.

You should also inform the staff at Rose Research Center if you believe you may be pregnant (for women only).

Use caution driving and operating machinery when you first start taking bupropion until you know how it is going to affect you. Some people feel dizzy or have trouble concentrating when they first start bupropion.

### Potential Side Effects

In some people, bupropion can cause:

Dry mouth	Insomnia (trouble sleeping)
Unusual dreams	Mood changes
Headaches	Constipation (hard to poop)
Change in appetite or weight	Excitement or anxiety

If you experience any of these side effects, or any other side effects, please notify the staff at Rose Research Center.

## INSTRUCTIONS FOR PROPER USE OF ZONISAMIDE (ZONEGRAN)

### How does it work?

This medicine is normally used to prevent seizures, but it may help with switching to sole use of an electronic cigarette.

### How do I take this medicine?

1. Take zonisamide exactly as directed. The blister packs are designed to help you take the medicine properly.
  - a. Take 2 capsules (50 mg each, total of 100 mg) in the morning.
  - b. Only change your medicine at the direction of the study personnel or if you have a serious concern.
2. Do not take this medicine if you have a severe allergy to sulfa drugs (like Bactrim, Septra, Diabeta).
3. Do not crush, chew, open or split the capsule.
4. Take zonisamide with a full glass (8 ounces) of water. Zonisamide can be taken with or without food (do NOT drink alcohol with zonisamide).
5. We will schedule you to start taking zonisamide about 7 days before your actual switch date (the day you stop smoking and only use the electronic cigarette).
6. If you forget to take a dose of zonisamide, take it as soon as you remember. If it is almost time for your next dose (less than 6 hours), just wait and take your next dose at the regular time. Do NOT take an extra dose to make up for the dose you forgot.
7. Keep this medication in a safe place, AWAY FROM CHILDREN. It should be stored at room temperature (not in your car) and away from direct sun, excessive heat, cold, or moisture. You MUST return any unused medication.

### Precautions

Some people have reported changes in behavior, agitation, depression, thoughts of suicide, or hostility. If you experience any of these issues, please call Rose Research Center and speak with one of our helpful staff [contact]). You may also call the 24-hour emergency advice line and speak with our study physician [contact]) if you feel this is an emergency.

As with most any medication, there is a risk of having an allergic reaction to zonisamide. This can be serious, especially if you experience swelling of the face, mouth, tongue, or throat which causes difficulty breathing. If you have any of these symptoms, stop taking zonisamide and get medical attention right away. Inform the staff at Rose Research Center AFTER you obtain medical care for these symptoms.

You should tell the staff at Rose Research Center if you have any allergies to medicines, including zonisamide or sulfa drugs.

You should also inform the staff at Rose Research Center if you believe you may be pregnant (for women only).

Use caution driving and operating machinery when you first start taking zonisamide until you know how it is going to affect you. Some people feel sleepy, dizzy, or have trouble concentrating when they first start zonisamide.

### Potential Side Effects

In some people, zonisamide can cause:

Nausea (feel like throwing up)	Drowsiness
Dizziness	Heartburn
Headaches	Constipation (hard to poop)
Weight loss	Dry mouth

If you experience any of these side effects, or any other side effects, please notify the staff at Rose Research Center.

